8. PARTICIPANT SELECTION AND RECRUITMENT

The proposed process for participant selection and recruitment to be adopted for the research study is:

- The site trial coordinator/research nurse/midwife will identify women who may be eligible for trial participation.
- Eligible women will be invited to participate by the site trial coordinator/research nurse/midwife (researcher). The researcher will introduce themselves and the research environment of the hospital and university. The researcher will explain that the mother is identified as potentially suitable for participation in this research project and seek the mother's permission to describe the research project to her
- Provide the mother with the Participant Information and Consent Form (PI&CF) for the research project
- Give a full verbal explanation of the purpose of the research project and a comprehensive description of what their participation entails, covering all elements that are stated in the Participant Information sheets
- Inform the mother that participation in this, and any other, research project is voluntary, and her clinical care will not be affected if she chooses to decline
- Encourage the mother to ask questions about the research project and to discuss it with their partner/family/doctor/midwife or any others of their choosing, before making a final decision
- All women will be given as much time as they require to fully consider whether they enrol. Contact telephone numbers of a researcher(s) will be provided for any questions that the woman would like answered in the interim.

- h) The researcher will meet the women again and, if she wishes to participate in the trial and remains eligible, written, informed consent will be obtained by the researcher(s) once the researcher is satisfied that the mother understands the implications of participating in the study
- i) The participant's consent to share data between the research and clinical teams for neonatal and/or paediatric assessments that are commonly performed across multiple studies or for clinical care will be discussed and she will be asked to sign a separate consent form for this data sharing process.
- j) Provide a copy of the signed Consent Form, together with the Participant Information sheets to the now participant
- k) Place a signed copy of the Consent Form and Participant Information sheets in the medical records belonging to the participant
- l) Keep the original signed Consent Form on file in the trial office for verification and audit purposes
- m) No trial related procedure(s) will be undertaken until the consent process has been completed
- n) Consent is an ongoing process throughout the trial. The researcher(s) will communicate with the participant throughout. Verbal consent will be obtained before the administration of the trial intervention (tablets) as well as for any other trial-related procedures, e.g. venepuncture and collection of, per protocol, blood samples
- o) For those women who decline to take part in the trial, their routine antenatal care will not change. Melatonin is not available as part of this standard of care.

9. RANDOMISATION

Randomisation will be via an on-line computerised randomisation service. Randomisation will occur on a 1:1 ratio of melatonin to placebo with the goal of 83 participants randomized to each of the two trial arms stratified by gestational age at recruitment and the presence or absence of abnormal Dopplers. At the time of recruitment, each participant will be assigned a unique trial code. Subsequently, all data and tissue samples collected from the participant will be stored only with this associated code. Thus, all data and tissue samples are deidentified at the point of collection, but with the capability to re-identify them in the future for data verification, research audit or safety (e.g. needle-stick injury).

Furthermore, it will be possible to break the randomization code and reveal treatment group if necessary, such as in the event of a potential treatment-related serious adverse event occurring.

10. TRIAL STUDY GROUPS

10.1 – Trial Study Groups

Once informed, written consent has been obtained, participants will be stratified by gestational age. Hereafter, participants will subsequently be randomized into one of two groups to receive the trial intervention, either:

1. Melatonin
10mg melatonin tablets, administered three times a day (tds) (a total daily dose of 30mg per day) **or**
2. Placebo
Visually identical placebo tablets containing no active ingredient, administered three times a day (tds)

Participants, their healthcare providers and the research team will be blinded to the trial intervention the participant has received throughout the trial and during follow-up of the children until all participants have completed all the stages of the trial as per protocol.

10.2 – Drug Supply and Storage

Melatonin 10mg tablets with a Certificate of Analysis will be sourced by Akesa Pharma (Melbourne, Australia). A matched placebo will then be produced by the Pharmaceutical Packaging Professionals (Port Melbourne, Australia), who will repack all trial medication to maintain blinding and manage its storage and distribution. Trial medication will be supplied in bottles containing 42 tablets to cover trial medication for a 2-week period. Trial medication will then be dispensed to participating sites designated trial pharmacies for dispensing to the individual trial participants on a fortnightly basis.

11. DURATION OF ADMINISTRATION OF THE TRIAL INTERVENTION

11.1 – Duration of Trial Intervention

The administration of the trial intervention i.e. melatonin or placebo tablets, will commence after informed, written consent has been obtained. Participants will continue to take the trial tablets, per protocol, three times daily (tds) until delivery at which time administration will immediately cease.

11.2 - Indications to cease administration of the trial intervention

1. Delivery of fetus
2. Request by the Principal Investigator responsible for trial-related medical decisions, for example, following a serious adverse event (SAE) or adverse event that is assessed by the PI, as being directly related to the administration of the trial intervention or as a consequence of trial participation.
3. Request by the Human Research Ethics Committee/Research Directorate
4. Recommendation by the Data Safety and Monitoring Committee (DSMB)

5. Participant request

12. PARTICIPANT TRIAL SCHEDULE

Participant flow through the trial is demonstrated in figure 2.

[figure not shown]

Figure 2: Individual Participant Trial Schedule. Investigations during fetal life will be performed as outlined until birth occurs. 3m = 3 months and 24 - 36m = 24-36 months corrected age. Note, some of the biological sample collections are optional.

12.1 Baseline data collection

Data for each participant will be collected, including details of age, ethnicity, height and weight, BMI, past obstetric history, past medical history, medication use, details of aneuploidy screening and invasive tests and fetal infection screen.

Previous USS data will be collected for growth, liquor volume, anatomy scan details and uteroplacental and fetal Doppler indices (where done).

12.2 Participant surveillance

Blood pressure measurement, maternal weight and urinalysis (dipstick for proteinuria) will be performed fortnightly. Ongoing monitoring for adverse effects will occur through the use of questionnaire and participant medication diary. Assessment of the newborn sleep patterns will occur over the first week after birth with a parent completed sleep-wake diary.

12.3 Participant blood tests and tissue samples

Full blood count, renal (urea, electrolytes, creatinine, urate) and liver (ALT, bilirubin, albumin) function will be tested before the commencement of treatment, 48 hours +/- 24 hours and 14 days (+/- 2 days) after commencement of trial medication and on the day of delivery. Results will be available to the treating clinical team.

Maternal and umbilical cord blood samples will be collected at the time of delivery for assessing melatonin concentrations within both the maternal and fetal circulations respectively. These results will not be available to the treating team.

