To evaluate the maternal-fetal transfer of melatonin Okatani et al. (1998) ³⁷ administered a single oral dose of 3mg melatonin to 33 women at term (37-40 weeks gestation) 1- to 4-hours before a planned caesarean section. Levels of melatonin were evaluated in maternal venous blood and umbilical venous and arterial blood. A total of 12 healthy pregnant women delivered by vaginal birth served as controls. Administration of melatonin led to a rapid (<120 minutes) and marked (>20-fold) increase in the fetal serum levels. There were no differences between maternal and fetal serum levels of melatonin, suggesting a rapid and unrestricted transfer of melatonin from mother to fetus.

The same authors tested whether melatonin could up-regulate antioxidant enzymes ³⁷. No longer than 12 hours before voluntary termination of pregnancy (between 7- and 9-weeks gestation), an oral dose of 6mg melatonin was administered to 47 pregnant women. A significant increase of the antioxidant enzyme glutathione peroxidase was observed in chorionic homogenates derived after the procedure, leading to the conclusion that melatonin might provide an indirect protection against injury caused by reactive oxygen species as seen in preeclampsia, FGR and fetal hypoxia.

The dose used in this trial is based on data from a clinical trial of melatonin for preeclampsia ³⁸ showing that 30mg per day was safe for mother and baby without any apparent adverse effects ³⁹. Venous cord blood concentrations of melatonin achieved were unchanged between a mother receiving 8mg and 30mg per day of melatonin (melatonin concentration ~2100pg/mL). This cord blood concentration would appear sufficient for neuroprotection according to information in sheep models. However, the degree of oxidative stress reduction achieved within the placental bed was less in mothers receiving 8mg melatonin per day. As such, it was felt that the higher dose of 30mg per day was more likely to achieve a clinically significant result.

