24. APPENDIX 1 - ADDITIONAL RESEARCH COMPONENTS

In addition to the trial outlined above, there will be further research elements also undertaken at Monash Health. Other participating institutions are welcome to undertake these further components and contribute to data collection.

24.1 – Additional Secondary Aims

These are:

1. To assess biomarkers of oxidative stress and melatonin levels within the maternal, fetal and placental compartments.

These additional research components would be incorporated into the individual participant trial schedule (as outlined in figure 1).

24.2 – Additions to the Individual Participant Trial Schedule

24.2.1 - Maternal blood tests

Further blood samples will also be collected at the time of maternal sample collection as outlined in section 12.3 (recruitment, 48 hours and 14 days). The total blood sample volume collected will not exceed 20 ml. These samples will be used for assessment of circulating melatonin levels and markers of oxidative stress.

These results will not be available to the treating clinical team.

24.2.2 – Participant tissue samples.

Following birth (20 minutes), placental samples will be collected as described in section 12.3.

All tissue samples will be collected without compromising or obstructing a participant's clinical care, at all times participant well-being and treatment will remain the priority.

The researcher is responsible for the collection and de-identification of all tissue samples, as site storage at -80°C until recruitment has been completed. The lead trial team will be responsible for subsequent transportation to Monash Medical Centre for analysis.

The samples will be collected and processed with researchers blinded to the intervention that the participant has received and neurodevelopmental outcome assessments.

Using each participant's unique code, tissue samples will be reconciled with the intervention that the participant has received only at the time of data analysis.

The tissue samples will be used for measuring melatonin levels within the maternal and placental circulations. Markers of oxidative stress, such as malondialdehyde and 8hydroxyguanosine, will also be assessed to determine the potential action through which melatonin is exerting its effects.

24.2.3 – Neonatal Cardiac and Cerebrovascular Assessment

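### Melatonin concentrations can indicate the arm for many women, yet they are expressly withheld only from the treating team, and laboratory work is scheduled 18–24 months before follow-up ends

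*Protocol*

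**What the plan says.** **Blinding rule.** Section 10.1: "Participants, their healthcare providers and the research team will be blinded to the trial intervention the participant has received throughout the trial", and it extends this through the children's follow-up until all participants have completed all stages.

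**Who is denied melatonin results.** Section 12.3, on maternal and cord blood taken at delivery: "These results will not be available to the treating team". Section 24.2.1 adds maternal samples at recruitment, 48 hours and 14 days ("These samples will be used for assessment of circulating melatonin levels and markers of oxidative stress") and says: "These results will not be available to the treating clinical team". Neither section mentions the research team.

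**Sample handling.** Section 24.2.2 keeps samples "as site storage at -80°C until recruitment has been completed", after which they go to the lead centre for analysis. It also says: "The samples will be collected and processed with researchers blinded to the intervention that the participant has received and neurodevelopmental outcome assessments", and that "tissue samples will be reconciled with the intervention that the participant has received only at the time of data analysis". That section covers melatonin in the maternal circulation, so its storage rule appears to include blood.

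**Data access.** Section 12.8 limits the electronic data to the named principal investigators and the trial researchers. No section keeps melatonin results out of that database.

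**Timetable.** Section 18: recruitment May 2019 to December 2023; laboratory analysis of melatonin's impact on oxidative stress, and a safety and tolerability analysis, January–June 2024; follow-up complete December 2025; data analysis complete January–April 2026.

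**The concern.** Holding back the allocation code is an adequate safeguard for a marker that says little about the arm. It is weaker for the concentration of the study drug. Section 2.5 reports, for a single 3 mg dose: "Administration of melatonin led to a rapid (<120 minutes) and marked (>20-fold) increase in the fetal serum levels". A list of concentrations keyed only by trial code could therefore point to the arm for many women without the randomisation list being opened.

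If such a list exists while children are still being followed, the research team's blind under section 10.1 rests on a general statement with no mechanism behind it. The work exposed is what that team still has to do: tracing and retaining families for the 24–36 month visit, judging the causality of late adverse events (16.4), and deciding what is reported (16.5.3 leaves adverse-event reporting to the investigator's discretion; 16.9 lets the lead investigator set aside events judged unrelated). Section 16.1 records adverse events until about 2 years corrected age.

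**Working it through.** **Step 1. Set the passages side by side.**

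| Question | Section 10.1 | Sections 12.3, 24.2.1, 24.2.2, 18 |
|---|---|---|
| Who must not know the arm? | Participants, providers, research team | Melatonin results expressly withheld from the treating team only |
| Until when? | All participants have completed all stages | Samples linked to the code at data analysis; site storage ends at close of recruitment |
| Dates implied | Not before December 2025 | Laboratory and safety work January–June 2024 |

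From the start or end of that laboratory window to December 2025 is 24 or 18 months. If either 2024 analysis is done by arm, linkage at data analysis comes 18–24 months before section 10.1 allows it.

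**Step 2. How many primary assessments are still to come?** The protocol gives no figure for this, so there is none to reproduce. The inputs are:

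- Recruitment May 2019 to December 2023 inclusive: 8 + 4 × 12 = 56 months (section 18).
- Gestation at entry 23+0 to 31+6 weeks (section 6.1).
- Bayley-4 and ITSEA at 24–36 months corrected age (section 12.5).
- Planned total 332 (section 7: 4 × 69 = 276, plus 42 and 14).
- Assumptions: even accrual, and corrected age counted from 40 weeks.

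Lag from entry to the visit = (40 − gestation at entry) weeks + visit age.

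- Entry at 23+0: 17 weeks / 4.345 = 3.9 months, so 27.9 months to age 24 months.
- Entry at 31+6: 8.1 weeks / 4.345 = 1.9 months, so 25.9 months.

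Share not yet at the visit age = (lag − months since recruitment closed) / 56.

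| Date | Visit at 24 months | Visit at 36 months |
|---|---|---|
| Recruitment closes | 25.9/56 = 46% to 27.9/56 = 50% | 37.9/56 = 68% to 39.9/56 = 71% |
| Six months later | 19.9/56 = 36% to 21.9/56 = 39% | 31.9/56 = 57% to 33.9/56 = 61% |

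On 332 women, before perinatal loss and drop-out, the 24-month column is 153–165 at close of recruitment and 118–130 six months later. The 36-month column is an upper bound: it assumes that every child is seen at the very end of the window.

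**Step 3. How far can a concentration disclose the arm?** The more than 20-fold rise was seen when women were dosed 1–4 hours before a planned caesarean. This trial fixes no interval between the last tablet and sampling. Section 2.4 describes low daytime and high night-time natural secretion. Section 2.5 also reports cord concentrations unchanged between 8 mg and 30 mg a day, so the larger dose here is no ground for expecting a larger signal. Only the delivery samples are trial-wide. The earlier ones belong to an appendix that other sites may choose to join, and some collections are optional (legend to Figure 2). A recruitment sample taken with the baseline bloods precedes treatment and serves only as a reference value. The documents give no placebo distribution, so the proportion correctly classified cannot be computed; many, but not all, is as far as they go.

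**The case against.** The strongest reply is that this argues from silence. No section gives individual melatonin results to the research team, section 10.1 blinds that team, and section 24.2.2 has samples processed by blinded researchers. Anyone applying 10.1 strictly would already keep revealing results away from the team. It stands that the defect is a missing safeguard and not a stated release. It does not dispose of the point, because the only sentences that deal with these results name a narrower group, and the delayed-linkage rule does not do its job for this analyte.

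The timing is also partly inferred. The 2024 laboratory entry in section 18 names oxidative stress, not melatonin levels. Section 24 pairs the two assays on the same samples, which makes the inference reasonable but not certain.

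Some stronger readings are tempting and not supported:

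- That the assay reveals every woman's allocation. Step 3 of the working shows why it cannot be relied on to do so.
- That the primary outcome is biased. Section 12.5.3 blinds the Bayley-4 psychologist to treatment group, and no stated route carries assay results to that person.
- That ITSEA is compromised. Parents complete it, nothing gives them results, and the psychologist analysing it is blinded to treatment group.
- That prescribing is affected. Tablets stop at delivery, so very little prescribing remains once recruitment has closed. For the same reason most adverse events during exposure will already have been judged, and section 16.9 keeps details of events that are not reported.

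**Conclusion.** The point holds as an unresolved inconsistency that creates a risk of functional unblinding. The blinding in section 10.1 is not carried through to the handling of melatonin results or to the timetable in section 18. Under even accrual, roughly a third to a half of 24-month assessments would be outstanding in the laboratory window, and more if visits fall late in the 24–36 month range. Those percentages count visits still to be made. They measure neither the number of women unblinded nor the size of any bias, and a different accrual pattern would move them. The documents do not support saying that the triple blind fails. What is exposed is follow-up effort and late adverse-event causality and reporting judgements, by an amount that cannot be quantified from the protocol.

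**What to change.** Reconcile sections 12.3, 24.2.1, 24.2.2 and 18 with section 10.1 by stating that:

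- individual melatonin results, and any by-arm laboratory or safety analysis, are withheld from all research staff in contact with families, assessments or adverse-event judgements, with the DSMC excepted, until the last Bayley-4/ITSEA is complete and the database is locked;
- this is achieved either by running the melatonin assay after lock, or by having the laboratory hold the results in a restricted file outside the trial database.

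The latest version listed in the protocol is dated July 2024, after the planned laboratory window. The amendment should therefore also record whether any melatonin assay has been run and, if so, who has seen individual results.

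The cost is a wording amendment and a restricted file, with no extra samples or participants. The small downside is later access to melatonin levels and by-arm mechanistic results.

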12.4 Ultrasound scans

All of the following measurements will be made on the day of recruitment, or within 3 days prior, and then ongoing as described:

- Fetal wellbeing assessment at 48 hours (+/- 24 hours) including amniotic fluid index (AFI), single deepest vertical pocket, umbilical artery (PI and presence/absence or reversed end diastolic flow), umbilical vein (pulsatile or non-pulsatile), ductus venosus (PI, presence of positive a wave), middle cerebral artery (MCA) PI and uterine artery PI.
- Fetal growth measurements: abdominal circumference (AC), biparietal diameter (BPD), head circumference (HC) and femur length (FL). Growth parameters will then be repeated on a fortnightly basis.
- Amniotic fluid measurement: four quadrant AFI and single deepest vertical pocket will be performed fortnightly.
- Doppler waveforms: umbilical artery (PI and presence/absence or reversed end diastolic flow), umbilical vein (pulsatile or non-pulsatile), ductus venosus (PI, presence of positive a wave), middle cerebral artery (MCA) PI and uterine artery PI will be performed fortnightly.

Scans are performed in routine clinical practice at this frequency for assessment and surveillance of severe FGR. Standard operating procedures will be supplied for trial purposes. The timing of scans stated here are required for trial purposes; it is likely that scans may be performed more frequently.

These assessments will continue until delivery and be performed blinded to treatment group. The ultrasound images will be collected using standard approaches and images reviewed to ensure appropriate. The ultrasound results will be available to the treating team to guide clinical decision-making. However, the clinical team will also be blinded to treatment group.

12.5 Neurodevelopmental Assessments

Neurodevelopmental assessments will be performed using a General Movement Assessment (GMA), magnetic resonance imaging (MRI), Bayley Scales of Infant and Toddler Development 4th edition (Bayley-4) and the Infant Toddler Social-Emotional Assessment (ITSEA). GMA and MRI will be performed at term corrected, GMA will be repeated a further two times at 3 months corrected age ± 2 weeks, while Bayley-4 and ITSEA will be performed at 24-36 months corrected age. If participants are enrolled in concurrent studies where the same assessments are involved, or if the clinical team has flagged for this assessment to be complete, patient data will be shared between research and/or clinical teams to minimise the inconvenience for the participants. The research team will seek formal consent for this data sharing arrangements from these participants.

12.5.1 - GMA

GMA is a non-invasive measure of spontaneous infant movement. Episodes of spontaneous movements are assessed via video recordings using established methodology⁵⁷, with movements classified as normal, abnormal, or absent depending on the gestational age of the

infant and number of weeks post birth. While a simple measure that is easily learned, it has been shown to be a clinically useful indicator of an individual's likelihood of developing cerebral palsy with high positive and negative predictive values. This assessment is not currently in routine clinical use across all health services. All GMA's will be collected using the Baby Moves App (Murdoch Children's Research Institute) and assessed by assessors blinded to treatment group. One GMA will be collected at term equivalent, then two separate video's collected at 3 months corrected age a couple of weeks apart to assist the GMA assessors in reliably determining a reduction or absence of fidgety movements. For sites where the GMA is part of routine care and with established clinical follow-up pathways in place, GMA results will be available to the treating team and additional interventional care offered if indicated, as is usual practice at Monash Health. The research team will not be involved in this care or the decisions regarding the need for interventional therapy. However, at sites where the GMA is not clinically used, results will not be disclosed.

12.5.2 – MRI

MRI will be performed of the infant with a 'feed and wrap' technique. High-resolution axial imaging using T1, T2 and DWI sequences will be obtained. Diffusion tensor imaging (DTI) will be used to study white matter tract microstructure. This technique allows calculation of fractional anisotropy (FA), axial diffusion (AD) and radial diffusion (RD) of cerebral white matter tracts.

For sites contributing to the MRI specific study, a standard operating procedure will be provided including a scanning protocol. Each site will nominate a local radiologist for clinical reporting. All MRI studies should be reported by a single radiologist at each site blinded to treatment group. The MRI results will be available to the treating team to guide clinical decision making, the clinical team will also be blinded to treatment group. Each site will be responsible for the development of a local plan for the management of potential incidental findings and the local site team will take responsibility for sharing results with families and arranging any ongoing investigations and/or care.

To enable the detailed analysis of the white matter tract microstructure, acquired de-identified MRI data in digital form of DICOM files (there will be no hardcopy films) will be securely transferred to Commonwealth Scientific and Industrial Research Organisation (CSIRO) using CloudStor, the secure file transfer solution hosted on the AARNet network (Australia's national research and education network). Transferred data will be securely stored at CSIRO's servers which are directly managed by CSIRO's central Information Management and Technology department and ensures an extremely high level of data storage safety (multiple backups) and confidentiality (encryption, strong access controls). This will be for a term of 15 years, in keeping with the NHMRC's guidelines on responsible conduct of research. This is readily achievable thanks to the enormous storage capacity in CSIRO's servers. A copy will be stored in CSIRO's Australian E-Health Research Centre's (affiliation of the investigators of the project) Xnat and RedCap database. Similar very high levels of data storage safety and confidentiality are implemented for the Xnat and RedCap databases as for CSIRO's servers.

The results from the analysis of the white matter tract microstructure will not be made available to clinical treating teams, as this is not an analysis that is in clinical use.

12.5.3 - Bayley-4

The primary outcome is a clinically meaningful difference in cognitive development at 24-36 months corrected age identified by a change in the Bayley-4 Cognitive score of 5 points. We will administer the cognitive, language and motor domains of the Bayley-4. The Bayley-4 is a direct assessment of neurodevelopment and will be performed by an experienced paediatric developmental psychologist blinded to (i) treatment group and (ii) GMA scores. Any concerning results will be discussed with the family and when appropriate referral onto appropriate specialists/services made.

12.5.4 – ITSEA

The ITSEA assesses a wide array of social-emotional and behavioural problems and competencies. It is validated for use between 12-36 months of age and will be applied to our trial cohort at 24-36 months corrected age. It is a parent-reported assessment undertaken in the form of a questionnaire. Results will be analysed by an experienced paediatric developmental psychologist blinded to treatment group, GMA and Bayley-4 data.

Any concerning results will be discussed with the family and when appropriate referral onto appropriate specialists/services made.

